5.1.2 Inpatient Data Collection

After enrollment and randomization, the following data will be collected from the EMR while the patient is in the hospital:

- Birthweight
- Birth hospital
- Date of transfer to CHOP,HUP, of PAH (if applicable)
- Antenatal steroid treatment
- Reason for preterm birth
- Respiratory support
- Growth parameters at 36 weeks PMA
- Growth parameters at 40 weeks PMA
- Treatment with the following medications for BPD: iNO, postnatal steroids, inhaled bronchodilators, inhaled steroids, other
- Any surgeries
- Neonatal morbidities (surgical NEC, PDA ligation, ROP surgery, etc).
- Screening for pulmonary hypertension

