5.1.4 Outpatient Data Collection

During the remainder of the study period, the following data will be collected:

- Rehospitalizations: location, duration, and ICU care, primary reason for hospitalization
- Medication use
- Visits to doctor or emergency room, with reason
- Procedures or surgeries
- Growth parameters as assessed at any clinical visit(s)
- Mode of feeding
- Developmental assessment (Bayley screener)

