5.3 Safety Evaluation

Subject safety will be monitored by adverse events, as well as the clinical outcomes as described above. Potential adverse clinical outcomes based on the prior literature are pneumonia/BPD exacerbations and detrimental effects on parental quality of life.

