6.2 Secondary Endpoints

All secondary endpoints in this pilot study are essentially exploratory and descriptive. The primary clinical outcome is growth in kilograms between 36 weeks PMA and 6 months CA. In addition, the study will also report:

- The change in other growth parameters - length (cm), weight for length, and head circumference (cm) - between 36 weeks PMA and 40 weeks PMA, 3 months CA, and 6 months CA.
- Differences between groups on a standardized feeding questionnaire at 3 and 6 months CA.
- Differences between groups in parent and child quality of life at 3 and 6 months CA.
- Differences between the groups in health care utilization at 3 and 6 months CA.
- Differences between the groups in development at 6 months CA.
- Safety, assessed as differences in growth, re-hospitalizations, and any safety events at 3 and 6 months CA.

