6.3.3 Safety Analysis

All subjects entered into the study will be included in the safety analysis. The frequencies of AEs by type, body system, severity and relationship to study arm will be summarized. SAEs (if any) will be described in detail.

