9.4.2 Risk Assessment

Confidentiality. Protected health information will be collected as part of study records, and breaches of this information outside of the study team resulting in loss of confidentiality is a potential risk. Every precaution will be taken to secure participants' personal information to ensure confidentiality. Our institution maintains strict policies, systematic procedures and sufficient resources for data management in compliance with HIPAA and IRB regulations for safeguarding participant information. Electronic data will be stored in secure, password-protected systems. Paper data will be stored in a locked cabinet in the locked Neonatology office suite at CHOP. Participants will be assigned a unique identifier that contains no protected health information. Access to the identifiers of the coded data will be controlled by the PI and only study team members will have access to the electronic and paper data.

Saturation Targeting. Targeting high oxygen saturations with supplemental oxygen may be associated with increased pulmonary oxygen toxicity, retinopathy of prematurity, decreased quality of life, without improving neurologic outcomes. Targeting lower oxygen saturation ranges with less supplemental oxygen may be associated with more episodes of hypoxia which might impact growth and development. Subjects will be monitored simultaneously with a clinically indicated pulse oximeter monitor. There are subject discontinuation and study stopping criteria as well as monitoring procedures in place and, in addition to the PI, an independent monitor will conduct data safety monitoring.

Oxygen saturation monitors. Oxygen saturation monitors are routinely used in the NICU and also frequently indicated for home use in infants with BPD. Participants will follow routine clinical routines for frequent site relocation of the oximeter sensors (probes), which will eliminate the risk of any significant skin irritation. The monitor will have an alarm, which will sound if the sensor is not working or if the infant's oxygen level is too low, which may be bothersome to families.

Questionnaires. Risks are not greater than minimal. Completing questionnaires in regards to health behavior activities could potentially be distressing for some parents/caretakers, however it is not likely that these activities will create additional distress beyond that which is already present.

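### Re-hospitalisations compared at fixed corrected ages depend on when the first discharge falls, and ROP, a risk the protocol itself names, is not a named safety comparison

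*Combined protocol and SAP*

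**What the plan says.** Section 6.2 lists, among endpoints it calls exploratory and descriptive, "Safety, assessed as differences in growth, re-hospitalizations, and any safety events at 3 and 6 months CA". Section 6.3.2 assigns the remaining exploratory outcomes to simple two-group tests and states no person-time method or offset.

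The assigned target starts in hospital. Section 3.1.2 keeps the study alarm settings in place until the infant goes home, and section 9.1.2 says that families and research staff know the assignment. Section 5.1.3 collects the discharge date. Section 5.1.4 collects "Rehospitalizations: location, duration, and ICU care, primary reason for hospitalization".

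On ROP, section 9.4.2 says that targeting high saturations may be associated with "increased pulmonary oxygen toxicity, retinopathy of prematurity, decreased quality of life, without improving neurologic outcomes". Section 5.3 reads: "Potential adverse clinical outcomes based on the prior literature are pneumonia/BPD exacerbations and detrimental effects on parental quality of life". It does not mention ROP, and neither does the list in 6.2. The data items that would hold ROP information are "Neonatal morbidities (surgical NEC, PDA ligation, ROP surgery, etc" in section 5.1.2 and "Procedures or surgeries" after discharge in section 5.1.4.

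**The concern.** The intervention begins before first discharge, while the clock for re-hospitalisation begins at first discharge and stops at a fixed corrected age. Date of first discharge is therefore a post-randomisation variable that sets the exposure time of a safety outcome. A BPD exacerbation that leads to admission from home adds to the count, whereas the same event during a prolonged first stay does not. An infant who dies stops contributing. An infant still in the first stay at 3 months CA necessarily scores zero at that visit. If stays or deaths differ between arms, a lower count need not mean better safety.

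The ROP gap is of a different kind. The protocol names the risk when it weighs harms, but plans no comparison of it by name. It lists no eye status at randomisation and no later examination result. Section 6.3.2 says the exploratory analyses are meant to inform later studies, so either weakness could carry forward into the design of a larger trial.

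**Working it through.** **Re-hospitalisations.** The documents give no re-hospitalisation rate, length of stay or ROP rate, so there is no figure of the plan's own to reproduce. The inputs below, apart from the assessment ages, are assumptions.

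- Assessment ages from section 6.2: 3 and 6 months CA. At 4.345 weeks per month these fall 13.0 and 26.1 weeks after 40 weeks PMA.
- Assumed first discharge in the shorter-stay arm: 40 or 42 weeks PMA.
- Assumed extra first stay in the other arm: 2 or 4 weeks.
- Assumed equal and constant hazard at home, so that expected events are proportional to time at risk.

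Time at risk = assessment age − age at first discharge. Ratio = time at risk in the longer-stay arm / time at risk in the shorter-stay arm.

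| First discharge (PMA) | Extra stay | Weeks at risk to 3 months CA | Ratio | Weeks at risk to 6 months CA | Ratio |
|---|---|---|---|---|---|
| 40 weeks | 0 | 13.0 | 1.00 | 26.1 | 1.00 |
| 40 weeks | 2 weeks | 11.0 | 0.85 | 24.1 | 0.92 |
| 40 weeks | 4 weeks | 9.0 | 0.69 | 22.1 | 0.85 |
| 42 weeks | 0 | 11.0 | 1.00 | 24.1 | 1.00 |
| 42 weeks | 2 weeks | 9.0 | 0.82 | 22.1 | 0.92 |
| 42 weeks | 4 weeks | 7.0 | 0.64 | 20.1 | 0.83 |

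By 6 months CA the longer-stay arm therefore shows 8-15% fewer expected events with discharge at 40 weeks and 8-17% fewer with discharge at 42 weeks, with no true difference. By 3 months CA the deficits are 15-31% and 18-36%. Widening the assumed discharge age to 38-44 weeks moves the 6-month ratio for a 2-4 week difference to between 0.93 and 0.82.

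In infants: suppose 40% of the shorter-stay arm is re-hospitalised by 6 months CA with discharge at 40 weeks. The weekly hazard is −ln(0.60)/26.07 = 0.0196. The longer-stay arm then shows 1 − exp(−0.0196 × 24.07) = 37.6%, or 1 − exp(−0.0196 × 22.07) = 35.1%. With 21 evaluable infants per arm (42/2) that is 8.4 against 7.9 or 7.4 infants, a gap of at most about one.

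Dividing by weeks at home returns a ratio of 1.00 under these assumptions, but only because the hazard was assumed constant and equal.

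**ROP.** Set side by side, the sections show:

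- 9.4.2 names ROP as a possible risk of the higher target.
- 5.3 and 6.2 omit it.
- 5.1.2 lists ROP surgery without a date, in a chart extraction that also holds facts preceding randomisation, such as birthweight and antenatal steroids. Surgery before and after randomisation cannot be told apart from that item.
- 5.1.4 picks up later surgery.
- No section lists an eye examination or a stage. Worsening that does not reach surgery depends on someone recording it as an adverse event.
- 6.3.3 says: "The frequencies of AEs by type, body system, severity and relationship to study arm will be summarized". That wording does not make clear that counts are tabulated by arm.

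Power for a named ROP comparison with 21 per arm, on assumed rates: 5% v 10%, 9%; 5% v 20%, 31%; 10% v 30%, 36%.

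**The case against.** The strongest reply is that re-hospitalisation is only one part of the safety picture. Adverse events are monitored throughout the study (section 8.1) and, in Table 1, are assessed from baseline onward. All subjects entered are in the safety analysis, and serious events are described in detail (6.3.3). Section 5.2.2 records hospitalisations with their duration, in wording not limited to re-admissions, and 6.2 compares health care utilisation. All of this stands. A reader might infer that in-hospital exacerbations and deaths vanish, or that an arm with more deaths would be reported as safer. The documents do not support that, because those events would be reported alongside the count. What is missing is a stated comparison that combines them from randomisation.

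Second, nothing in the documents shows that first stay will differ by arm. Infants may go home on oxygen (3.1.3), so a higher target need not delay discharge. The 2.5 v 5.7 weeks in section 1.3 is time on oxygen in an earlier trial, not length of stay. This also stands, and it makes the artefact conditional.

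Third, a reader might infer that ROP is not captured at all. That goes too far. The morbidity list in 5.1.2 is open-ended, later surgeries are collected, and worsening ROP fits the adverse event definition in 8.3. The direction is also uncertain. Section 1.3 cites an adjusted odds ratio of 0.72 (95% CI 0.52-1.01) for progression with supplemental oxygen, and links severe ROP to time below 80% saturation. Uncertain direction is a reason to report ROP by arm. It does not show that the higher target is harmful.

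**Conclusion.** The point holds in a conditional form. The re-hospitalisation count can favour the arm with longer first stays or more deaths, and the plan states no measure that guards against this. The size is about 8-17% fewer expected events by 6 months CA for a 2-4 week longer stay, and about 15-31% by 3 months CA with discharge at 40 weeks. These figures rest on assumed discharge at 40-42 weeks PMA and equal constant hazards. With equal stays and equal deaths the bias is zero. The documents do not support a claim that a longer stay will in fact be mistaken for a safety benefit.

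On ROP, the accurate statement is that a risk named in 9.4.2 is not named, graded or scheduled as a safety comparison, and that progression short of surgery is recorded only if someone reports it. These endpoints are exploratory, and no sample-size figure changes. This is a worthwhile and cheap improvement, not a flaw in the primary analysis.

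**What to change.** 1. In section 6.2, add days alive and out of hospital from randomisation to 6 months CA, by arm, together with length of first stay from randomisation, by arm. The discharge date (5.1.3), re-hospitalisation duration (5.1.4) and dated adverse event records (8.3) already supply the inputs. The window runs from about 7.4 months for randomisation at 34 weeks PMA to about 5.1 months at 43 6/7 weeks. It is fixed at randomisation, so it introduces no bias, but expressing the result as a percentage of each infant's window makes it easier to read. Report re-hospitalisations per infant-week at home only as a supportive description, since that rate conditions on having been discharged.

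2. In sections 5.1.2, 5.3 and 6.2, name ROP. Extract from the medical record the last eye examination before randomisation, the results of later clinical examinations, and any ROP treatment with its date. Report post-randomisation progression or treatment descriptively by arm.

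The cost is wording and a few extra chart-extraction fields, with no new examination, visit or participant. The ROP comparison will have low power (9-36% on the assumed rates) and should be labelled descriptive.

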3.1.3 Phase 2 – Outpatient monitoring

At the time of hospital discharge, as detailed below, families will be given a Masimo oximeter along with a device that will transmit the oximetry data back to the study team at CHOP. They will be instructed how to use the device nightly while the child is sleeping at home.

Infants who are discharged per clinical recommendations on supplemental oxygen will have frequent visits in the CHOP Pulmonary Clinic. Oxygen titration and weaning will be standardized according to the algorithm in Table 2, below.

Table 2: Home Nasal Cannula Flow Titration Algorithm*		
	HIGHER SpO₂ TARGET ARM ($\geq 96\%$)	LOWER SpO₂ TARGET ARM ($\geq 90\%$)
Criteria for INCREASING O ₂ flow rate	SpO₂ < 96% for > 10% of recorded time	SpO₂ < 90% for > 10% of recorded time
Criteria for MAINTAINING current O ₂ flow rate	SpO₂ $\geq 96\%$ for 90-95% of recorded time	SpO₂ > 90% for $\geq 90\%$ of recorded time but NOT > 94% for $\geq 90\%$ of recorded time
Criteria for WEANING O ₂ flow rate	SpO₂ $\geq 96\%$ for >95% of recorded time	SpO₂ > 94% for $\geq 90\%$ of recorded time

*Decisions will be made by assessment of recorded oximetry. A minimum of 4 days of data, with a minimum of 8 hours per day, will be required for analysis to make a wean. Oxygen flow rates will be decreased stepwise: 2 LPM – 1.5 LPM – 1 LPM – 1/2 LPM – 1/4 LPM – 1/8 LPM. Once the child is stable on 1/8 LPM, he/she will be weaned off for increasing duration of time: first 6 hours, then 12 hours per day, and finally off completely.

Downloaded oximetry data will be reviewed and decisions about weaning will be made each week by the study team (including [name] from the Division of Pediatric Pulmonology). In the home setting, weans may be performed as often as every week. If an infant loses >5% of body weight in any month, no oxygen weans will be made until the weight is regained. If an infant is discharged without oxygen or weans off but then meets the criteria for increasing flow on two subsequent recordings, the family will be instructed to attend pulmonary clinic for assessment and then home oxygen therapy will be instituted.

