4.2.1 Oxygen Saturation Monitoring

- While inpatient patients will have two monitors, a clinical monitor and a research monitor
- Alarm limits on the clinical monitor will be changed to reflect randomization assignment.
- Study oximeter will be placed on baby with the alarms off to ensure consistent data collection throughout.
- Orders in EPIC will be changed to reflect randomization

Data elements to be collected after enrollment and during the inpatient phase are listed in section 5. An interpreter will be used to administer questionnaires to non-English speaking subjects.

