6.3.2 Efficacy Analysis

The primary analysis will be based on an intention to treat approach and will include all randomized subjects. Interpretation and analysis of downloaded saturation data throughout the study will be managed in two ways. Saturation data will be cleaned, processed, and analyzed weekly. This will allow real-time assessments in order to ensure that the oximeter is being applied routinely and sufficient usable data are available. In addition, the data will be analyzed to determine whether the participant is having SpO₂ below the target range that would necessitate either increase in flow or medical attention.

Generalized estimating equations will be used for continuous primary outcomes such as frequency of IH and growth and logistic models for binary outcomes. Models will be adjusted for potential confounders that are significantly different in bivariate testing, because differences may exist despite randomization due to small sample size. Variables that will be considered for inclusion in the model are gender, gestational age, birth weight, race, small size for gestational age, and severity of BPD. The remaining exploratory outcomes will be compared between groups with simple bivariate tests such as t-tests and χ^2 tests. Exploratory subgroup analyses will be performed to evaluate the effect of the intervention on the gestational age and severity of BPD strata. Lastly, we will test for PMA week-specific differences between study groups through regression models controlling for key covariates, and using adjustments to account for multiple testing across PMA weeks. Given the sample size of this pilot study, we will likely not have sufficient power to draw definitive conclusions in these exploratory analyses; however, these approaches to the data are likely to be valuable in planning future studies.

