7 STUDY INTERVENTION

7.1 Description

We will randomize infants with moderate or severe BPD to lower (target SpO₂ of 90-94%) or higher SpO₂ target ranges (target SpO₂ of >=96%). The study team will then use novel technology to monitor infants starting at randomization, continuing after discharge and until 6 months corrected age, titrating supplemental oxygen to achieve these target SpO₂ ranges.

All trial participants will be provided with a study oximeter. Families will be instructed to use the study monitor continuously each night or when the baby is napping. The research monitor will stay in the child's sleep space and set with alarm limits of 79% and 101% and will be attached nightly when the infant is placed in the bed (in addition to the clinical monitor if prescribed). The research oximeter will be set for 2 second averaging and sampling. In addition, we will collect photoplethysmography (PPG) data at a rate not greater than 100 Hz to aid in identifying errors in the SpO₂, likely caused by motion artifact.

Infants enrolled in the current study who are discharged on home oxygen will be provided with standard clinical monitors by their home care companies, which will be set with alarm limits of 88% and 101%, and used with a frequency determined by the discharging clinician.

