8.6 Medical Emergencies

It is possible that a home monitor will alarm repeatedly for low saturations. In this case, the family will be instructed to contact the child's doctor and if necessary bring the child to the emergency room. Such events will be monitored closely and reported to the IRB as necessary according to the above guidelines about adverse event reporting.

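### How non-serious safety events come to notice may differ by arm, and the planned between-arm safety comparison makes no allowance for it

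*Combined protocol and SAP*

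**What the plan says.** **The comparison.** Section 6.2 lists among the secondary endpoints "Safety, assessed as differences in growth, re-hospitalizations, and any safety events at 3 and 6 months CA". Section 6.3.3 adds: "The frequencies of AEs by type, body system, severity and relationship to study arm will be summarized". Section 6.3.2 assigns the remaining exploratory outcomes to simple bivariate tests. None of these sections considers how an event was found, and 9.1.2 leaves participants and research staff unblinded.

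**Routes that depend on the arm.** In hospital (4.2.1): "Alarm limits on the clinical monitor will be changed to reflect randomization assignment". The numeric limits for each arm are not given. At home, the data review in 6.3.2 looks for saturations "below the target range that would necessitate either increase in flow or medical attention". Table 2 sets the trigger at below 96% in the higher arm and below 90% in the lower arm, in each case for more than 10% of recorded time. Under 3.1.3, an infant off oxygen who meets the trigger on two recordings is sent to pulmonary clinic.

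**Routes that depend on oxygen.** Section 3.1.3: "Infants who are discharged per clinical recommendations on supplemental oxygen will have frequent visits in the CHOP Pulmonary Clinic". Section 7.1 gives infants discharged on home oxygen a clinical monitor, "which will be set with alarm limits of 88% and 101%, and used with a frequency determined by the discharging clinician". Every infant has the research monitor, "set with alarm limits of 79% and 101" percent. For recurrent alarms with respiratory distress, 4.3.1 directs families of infants on oxygen to the pulmonary team, and families of infants off oxygen with mild symptoms to the pediatrician. On repeated low alarms at home, 8.6 says: "Such events will be monitored closely and reported to the IRB as necessary".

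**Routes common to both arms.** Table 1 schedules AE/SAE assessment at baseline, at discharge, weekly after discharge, and at 3 and 6 months CA. Section 9.7 expects contact with each family at least weekly. Section 5.2.2 takes visits and hospitalizations from the EMR where possible and checks them with the parents.

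**The concern.** An observed AE count is the true frequency multiplied by the chance of being noticed. If that chance depends on the arm, a difference in counts is not a difference in harm.

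Section 9.4.2 names different risks for the two targets: oxygen toxicity, retinopathy and reduced quality of life for the higher, more hypoxia for the lower. Section 5.3 names pneumonia and BPD exacerbations as expected harms, and mild respiratory illness is the kind of event that an extra call or visit brings to light. Unequal detection could create an apparent harm of one target or mask a real harm of the other.

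The safety picture will be used even though it is exploratory. Section 6.5 reviews accumulating safety data after 10 and 20 completed participants, and 6.3.2 presents the analyses as input to later trials. How an event first came to notice is hard to reconstruct if it was not recorded at the time.

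**Working it through.** The plan gives no safety event rate, detection probability or safety power, so there is no figure to reproduce. The check has four steps. Every rate and probability below is an assumption unless a section is cited.

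**1. Do the two home triggers treat the same infant differently?** Model one SpO2 trace as normal with mean m and SD s. The time below 96% is Φ((96−m)/s) and the time below 90% is Φ((90−m)/s); the trigger is met above 0.10.
- m = 96, s = 2: Φ(0) = 0.50 and Φ(−3) = 0.001. The trigger is met in the higher arm only.
- m = 93 to 98 in steps of 1, with s = 1.5, 2 and 3 (18 cases): higher arm only in 16; both in 1 (m = 93, s = 3: 0.841 and 0.159); neither in 1 (m = 98, s = 1.5: 0.091 and 0.000).

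This shows that the rules differ. It does not predict the number of flags per arm, because titration will move the traces apart.

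**2. Does the target influence oxygen status?** Table 2 allows weaning in the higher arm at 96% or more for over 95% of the time, and in the lower arm at above 94% for at least 90% of the time, which is easier to meet. In the earlier trial in infants oxygen dependent at 32 weeks (1.3), the median time until oxygen stopped was 5.7 weeks with the higher target and 2.5 weeks with the standard one. Both point to longer oxygen use in the higher arm. However, 4.3.1 leaves discharge on oxygen to clinical judgment.

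**3. What would unequal detection do to the comparison?** Let the true rates be equal. The common schedule finds a share c of events, and the extra routes find a share e of the rest. Then d = c + (1−c)e, and the apparent higher/lower ratio is d(higher)/d(lower).

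| c | e = 0.8 higher, 0.4 lower | e = 0.4 higher, 0.8 lower |
|---|---|---|
| 0.50 | 0.90/0.70 = 1.29 | 0.70/0.90 = 0.78 |
| 0.80 | 0.96/0.88 = 1.09 | 0.88/0.96 = 0.92 |
| 0.95 | 0.99/0.97 = 1.02 | 0.97/0.99 = 0.98 |
| 1.00 | 1.00 | 1.00 |

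With 21 infants per arm (42/2, from 6.4), a true event proportion of 40% and the first row's detection of 0.90 versus 0.70, the observed proportions are 0.40 × 0.90 = 36% and 0.40 × 0.70 = 28%. Exact binomial calculation then shows more affected infants in the higher arm in 65% of trials (ties 11%), against 44% (ties 12%) with perfect detection in both arms. An uncorrected chi-square test reaches p < 0.05 in 9% of trials, against 5%. With detection reversed, the higher arm shows more in 23%.

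**4. Which safety components are exposed?**
- Growth is measured on a common schedule: little exposed.
- Re-hospitalizations have the EMR and parent check: little exposed, although extra contact could lead to some admissions.
- Low-saturation events are well measured as IH, from one device at one threshold, but not if alarms or review flags are counted as events.
- Non-serious respiratory AEs and clinic visits are the exposed part.

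**The case against.** The strongest case against the concern has five parts. Home alarm limits are the same in both arms for each device. AEs are assessed weekly in every infant, and visits and admissions are verified. Hypoxia is already a primary endpoint, measured in all infants at one threshold. Nothing in the plan calls a Table 2 flag an adverse event, and a visit it prompts is part of the strategy under test. The secondary endpoints are described as exploratory.

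Most of this stands and limits the concern. It does not remove it. Who has the 88% monitor depends on oxygen status. Section 8.6 links repeated low alarms to AE reporting. The weekly AE assessment is a row in Table 1 with no description of how events are elicited, and by step 3 any imbalance disappears only if that assessment finds everything. Because extra visits may be a real consequence of the strategy, they are better labelled than discarded.

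A reader might go further and infer that the higher arm will show more harms even when true harm is equal. The documents do not support that. At common alarm limits, the arm with more hypoxia alarms more, and 9.4.2 expects that in the lower arm. Inpatient limits per arm are not stated, and the 90-94% range is bounded above as well as below, so inpatient alarm burden cannot be ranked.

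A reader might also size the bias from the weaning ages in 3.1.4. With the lower arm weaned at 2 months CA and the higher at 4.5, 1 − 2/6 = 67% and 1 − 4.5/6 = 25% of the period lies outside oxygen use. If 20% to 50% of non-serious events are noticed only through oxygen-linked contacts, the ratio is 1.10 (0.950/0.867) to 1.31 (0.875/0.667); at 3 versus 4 months it is 1.04 to 1.11. The arithmetic is right but the inputs are not the plan's. Those ages are literature averages, not arm-specific. The monitor and visits attach to discharge on oxygen, and nothing says they end at weaning. The missed share is invented.

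Nor does 4.3.3 end AE assessment early: it lets study monitoring stop, and AE assessment is a separate row of Table 1.

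**Conclusion.** The point holds as a possible difference in ascertainment, confined mainly to non-serious events and clinic visits. The documents establish that some routes to detection follow the assigned target or oxygen status, and that 6.2 and 6.3.3 compare arms without separating those routes from the common schedule. More contact in the higher arm is plausible.

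The net direction and size of any bias cannot be derived. The ratios in step 3 (0.78 to 1.29 if the common schedule finds half of events, 0.92 to 1.09 if it finds 80%) are illustrations on assumed detection, and run both ways. The gap should be closed because doing so is cheap and the information is hard to recover later. It does not undermine the primary endpoint.

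**What to change.** In 6.2 and 6.3.3:

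1. Compare low-saturation events between arms only from the research-oximeter recordings, at the IH and severe IH definitions of 5.2.1, per recorded night as that section already does. State that clinical alarms and Table 2 titration flags are not counted as safety events in this comparison. Section 5.2.1 writes more than 30 seconds where 6.1 writes at least 30, so use one wording.
2. Add one CRF field for how each AE was first identified: common Table 1 assessment, alarm or family call, or titration review or visit. Keep all AEs in the main tabulation by arm. Add a sensitivity comparison limited to SAEs plus AEs identified at the common Table 1 assessments, and show events found only through alarms or titration contacts separately by arm.

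The cost is a few sentences, one CRF field and one extra table, with no added infants, visits or procedures. Individual safety reporting and clinical care do not change. One limit remains: parents may mention at a weekly assessment something they learned from an alarm or visit, so the sensitivity comparison reduces unequal detection without removing it. That is a reason to keep it as a sensitivity comparison beside the full tabulation.
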